## 60 Day-Telephone Contact

 Telephone contact with patient or LAR not completed (Complete the Subject Deviation form)

	Date of Contact Attempt	Time (24hr)	Name of caller	Contact Occurred	Outcome if no contact
Contact Attempt #1	   /   /     MONTH D D Y Y Y Y	    TIME (0-2400) /		  Yes   No	  No answer   Left Voice message   Left Message w/ _____   Line Busy   Other: _____
Contact Attempt #2	   /   /     MONTH D D Y Y Y Y	    TIME (0-2400)		  Yes   No	  No answer   Left Voice message   Left Message w/ _____   Line Busy   Other: _____
Contact Attempt #3	   /   /     MONTH D D Y Y Y Y	    TIME (0-2400)		  Yes   No	  No answer   Left Voice message   Left Message w/ _____   Line Busy   Other: _____
Contact Attempt #4	   /   /     MONTH D D Y Y Y Y	    TIME (0-2400)		  Yes   No	  No answer   Left Voice message   Left Message w/ _____   Line Busy   Other: _____

Was information obtained directly from the study patient?  Yes  No

If No, name of person who provided information: \_\_\_\_\_

Relationship to subject: \_\_\_\_\_

Was this individual the Legal Authorized Representative?  Yes  No

SITE ID		PATIENT ID				LETTER CODE			

**Telephone Contact (continued)**

QUESTION(S) TO BE ASKED	
 Is the patient still alive?	 Yes  No
 Ambulating without assistance?	 Yes  No
 Need mechanical ventilation for any part of the day (other than treatment for obstructive sleep apnea)	 Yes  No
 Need supplemental oxygen	 Yes  No
 Location of patient	 Home  Acute Care Hospital  Rehab  LTAC  Supervised living

COMMENTS:

---

---

---

---

---

---

---

---

---

---

FORM COMPLETED BY: \_\_\_\_\_

DATE: 

MONTH		

 / 

D	D

 / 

Y	Y	Y	Y

									
SITE ID		PATIENT ID			LETTER CODE				

## 90 Day-Telephone Contact

 Telephone contact with patient or LAR not completed (Complete the Subject Deviation form)

	Date of Contact Attempt	Time (24hr)	Name of caller	Contact Occurred	Outcome if no contact
Contact Attempt #1	   /   /     MONTH D D Y Y Y Y	    TIME (0-2400) /		  Yes   No	  No answer   Left Voice message   Left Message w/ _____   Line Busy   Other: _____
Contact Attempt #2	   /   /     MONTH D D Y Y Y Y	    TIME (0-2400)		  Yes   No	  No answer   Left Voice message   Left Message w/ _____   Line Busy   Other: _____
Contact Attempt #3	   /   /     MONTH D D Y Y Y Y	    TIME (0-2400)		  Yes   No	  No answer   Left Voice message   Left Message w/ _____   Line Busy   Other: _____
Contact Attempt #4	   /   /     MONTH D D Y Y Y Y	    TIME (0-2400)		  Yes   No	  No answer   Left Voice message   Left Message w/ _____   Line Busy   Other: _____

Was information obtained directly from the study patient?  Yes  No

If No, name of person who provided information: \_\_\_\_\_

Relationship to subject: \_\_\_\_\_

Was this individual the Legal Authorized Representative?  Yes  No

SITE ID		PATIENT ID				LETTER CODE			

**Telephone Contact (continued)**

QUESTION(S) TO BE ASKED	
 Is the patient still alive?	 Yes  No
 Ambulating without assistance?	 Yes  No
 Need mechanical ventilation for any part of the day (other than treatment for obstructive sleep apnea)	 Yes  No
 Need supplemental oxygen	 Yes  No
 Location of patient	 Home  Acute Care Hospital  Rehab  LTAC  Supervised living

COMMENTS:

---

---

---

---

---

---

---

---

---

---

FORM COMPLETED BY: \_\_\_\_\_ DATE: 

MONTH			D	D	Y	Y	Y	Y	

SITE ID		PATIENT ID				LETTER CODE			

## Summary of Patient Outcomes

Form completed by: \_\_\_\_\_

			/			/						
MONTH				D D			Y Y Y Y				TIME (0-2400)	

Date of discharge/death:

			/			/						
MONTH				D D			Y Y Y Y					

Disposition

 Home without assisted breathing	 Home with assisted breathing
 Acute care hospital without assisted breathing	 Acute with assisted breathing
 NH/assisted living without assisted breathing	 NH/assisted living with assisted breathing
 Died prior to home without assisted breathing	 Died prior to home with assisted breathing

Was this patient permanently withdrawn from the trial before day 28?  Yes  No

DATE: 

			/			/						
MONTH				D D			Y Y Y Y					

Reason for withdrawal: Death ECMO Other SAE LAR choice Provider choice

Was patient discharged alive from the study hospital by day 90?  Yes  No

DISCHARGE DATE: 

			/			/						
MONTH				D D			Y Y Y Y					

If discharged prior to day 90 was the patient readmitted to an acute care hospital by study day 90?

Yes No READMISSION DATE: 

			/			/						
MONTH				D D			Y Y Y Y					

If in the cooling group did the patient complete the cooling protocol  Yes  No  N/A

If No, reason for early termination: \_\_\_\_\_

Total hours cooled: 

--	--	--

If in the control group did the patient receive hypothermia before day 28?  Yes  No

If Yes, study day cooling started 

--	--

 and ended 

--	--

and the range of temperatures during the cooling period: 

--	--

 . 

--

 to 

--	--

 . 

--

 °C.

Was the patient alive by study day 90?  Yes  No  Unknown

If NO, Date of Death: 

			/			/						
MONTH				D D			Y Y Y Y					

Cause of death (from discharge summary/discussion with ICU team):

 Respiratory failure	 Cardiac (arrhythmia, ACS, cardiogenic shock)	 Multi-organ failure
 Refractory shock	 Intraabdominal (perforation, compartment)	 Withdrawal of care
 Severe sepsis	 Neurological devastation	 Hemorrhage

SITE ID		PATIENT ID			LETTER CODE		

Unassisted breathing for  $\geq 48$  hours by day 28?  Yes  No

If Yes, enter first date UAB began: 

MONTH			D	D	Y	Y	Y	Y

Was patient extubated by day 28?  Yes  No

If Yes, enter date of extubation: 

MONTH			D	D	Y	Y	Y	Y

Did the subject undergo tracheostomy by day 28?  Yes  No

If Yes, enter date of tracheostomy: 

MONTH			D	D	Y	Y	Y	Y

Was the patient discharged/transferred to a non-ICU setting by day 28?  Yes  No

If Yes, enter date of discharge/transfer: 

MONTH			D	D	Y	Y	Y	Y

Was the patient receiving prone positioning at randomization?  Yes  No

If Yes, Study day when patient received final prone positioning: 

--	--

If No, did patient receive proning during the first 28 study days:  Yes  No

If Yes, study day proning started 

--	--

 and ended 

--	--

SITE ID		PATIENT ID				LETTER CODE			

**Ventilator days until UAB at home, death or day 90 is any day patient received assisted breathing except for <24hr related to procedure/surgery**

Patient achieved UAB?  No  Yes Date of 1st UAB: 

MONTH			D	D	Y Y Y Y				

Patient returned to assisted breathing  No  Yes Date of return to AB: 

MONTH			D	D	Y Y Y Y				

Patient achieved UAB again?  No  Yes Date of 2nd UAB: 

MONTH			D	D	Y Y Y Y				

Patient returned to assisted breathing again  No  Yes Date of return to AB: 

MONTH			D	D	Y Y Y Y				

Patient achieved UAB again?  No  Yes Date of 3rd UAB: 

MONTH			D	D	Y Y Y Y				

Patient returned to assisted breathing again  No  Yes Date of return to AB: 

MONTH			D	D	Y Y Y Y				

Patient achieved UAB again?  No  Yes Date of 4th UAB 

MONTH			D	D	Y Y Y Y				

- End of life decision making (for all pts alive and dead)
- No DNR decision made
  - DNR decision made-withhold only CPR (CR or PR)
  - DNR decision made-withhold life support and CPR
  - DNR decision made-withdraw life support
  - Diagnosis of brain death
  - Unknown/can't tell

- Was written consent obtained from the subject during hospitalization?  Yes  No, reason
- patient died
  - Patient never regained decision-making capacity
  - Patient declined further participation in study
  - Other

Did patient require dialysis during Study hospitalization?  Yes If yes, enter dates of first and last dialysis: Date of first dialysis: \_\_\_\_\_ Date of last dialysis: \_\_\_\_\_  No

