#### [1.4/ Abbreviations and Acronyms](#)

COVID-19: Corona virus disease-2019

CHILL: Cooling to Help Injured Lungs

ALI: Acute lung injury

TH: Therapeutic hypothermia

NMB: Neuromuscular blockade

ARDS: Acute respiratory distress syndrome

SOFA: Sequential organ failure assessment

VFDs: Ventilator-free days

P/F: Ratio of partial pressure of oxygen:fractional index of inhaled oxygen

OSI: Oxygen saturation index

ECMO: Extracorporeal membrane oxygenation

FRH: Febrile-range hyperthermia

MICU: Medical intensive care unit

UMMC: University of Maryland Medical Center

CRRT: Continuous renal replacement therapy

SAE: Serious adverse event

HSCTI: Human subject clinical trial information

LAR: Legally authorized representative

CRF: case report forms

CCU: Cardiac care unit

CCRU: Critical care receiving unit

CVP: Central venous pressure

CCC: Clinical Coordinating Center

DCC: Data Coordinating Center

CSPCC: Cooperative Studies Program Coordinating Center (in [name])

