### 10.10/ Day 28 Data CRF

- Record site ID code, 3-digit study ID, and the unique 3 letter identifier in the indicated fields at the top of the worksheet.
- Record your name and the date and time CRF was completed in the indicated fields in line 1.

- Indicate if still alive by checking appropriate “Yes/No” box on line 2 and if “No” record date and time of death in the indicated fields on line 3 and check the box next to the most appropriate cause of death (from the discharge summary and discussion with the ICU provider team).
- Indicate whether patient has received any mechanical ventilation in the past 24 hours by checking the appropriate “Yes/No” box on line 4. If “No,” record the date and time the patient last received mechanical ventilation in the appropriate fields.
- Indicate if patient is still in an ICU setting by checking the appropriate “Yes/No” box on line 5. If “No,” record the date and time the patient was last in an ICU and check the box next to the best description of the patient’s current location.
- Enter the total number of ventilator-free days in the first 28 days of the study on line 6:
  - If the patient is alive at day 28, enter the sum of ventilator-free days from all UAB periods recorded on the Unassisted Breathing CRF, otherwise enter 0.
- Enter the total number of ICU-free days in the first 28 days of the study on line 7:
  - If the patient is alive at day 28, enter the sum of ICU-free days from all ICU-free periods recorded on the ICU Discharge CRF, otherwise enter 0.

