## Unassisted Breathing Checklist (for Study Day 1-28)

A period of unassisted breathing is defined as  $\geq 48$  continuous UAB, which includes:

- 1./spontaneously breathing with face mask, nasal prong oxygen including high flow, or room air
- 2./T-tube breathing
- 3./tracheostomy mask breathing
- 4./CPAP  $\leq 5$  cm H2O without PS or IMV assistance
- 5./use of CPAP or BIPAP solely for sleep apnea management

Fill out one section for each continuous period of UAB lasting  $\geq 48$  hrs up through study day 28.

A ventilator-free day is defined as a day (0800 to 0800) without any assisted breathing except for assisted breathing administered for  $< 24$  hrs solely for a surgical or other procedure.

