**Calculation of 28-day Ventilator-free days (VFDs):**

- If patient is alive at 28 days, add ventilator-free days from all UAB periods from the UAB CRF. If the patient died before day 28, enter 0: 

--	--

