 Relation to study intervention	 Not related  Unlikely  Possible  Probable  Definite	 Not related  Unlikely  Possible  Probable  Definite	 Not related  Unlikely  Possible  Probable  Definite
 Action taken with study intervention	 Not changed  Hypothermia stopped  NMB stopped	 Not changed  Hypothermia stopped  NMB stopped	 Not changed  Hypothermia stopped  NMB stopped
 Other action taken	 None  Concomitant med  Discontinue from study  Other _____	 None  Concomitant med  Discontinue from study  Other _____	 None  Concomitant med  Discontinue from study  Other _____
 Outcome	 Fatal  Not recovered  Not resolved  Recovered/resolved  Recovered/resolved with sequelae  Recovering/resolving  Unknown	 Fatal  Not recovered  Not resolved  Recovered/resolved  Recovered/resolved with sequelae  Recovering/resolving  Unknown	 Fatal  Not recovered  Not resolved  Recovered/resolved  Recovered/resolved with sequelae  Recovering/resolving  Unknown
 Assessment made by (investigator name)			

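### ECMO, SAEs and provider choice are listed as reasons for permanent trial withdrawal with no rule keeping those patients in the analysis, and the ventilator-free-day rule can credit days on ECMO

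*Protocol*

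**What the plan says.** Line 4 of the Summary of Patient Outcomes form (protocol appendix) asks "Was this patient permanently withdrawn from the trial before day 28" and takes a date and a reason: "Reason for withdrawal: Death ECMO Other SAE LAR choice Provider choice". The Adverse Event form has a second route. Row 13, other action taken, includes "Discontinue from study", listed apart from the row 12 boxes for stopping hypothermia or NMB.

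VFDs are scored in two places. Section 10.10 says that for a patient alive at day 28 the site should "enter the sum of ventilator-free days from all UAB periods recorded on the Unassisted Breathing CRF, otherwise enter 0". Line 6 of the Day 28 Data Summary form says: "If the patient died before day 28, enter 0". The Unassisted Breathing Checklist gives the daily rule: "A ventilator-free day is defined as a day (0800 to 0800) without any assisted breathing", with an exception for short procedures. It lists five modes that count as unassisted, the first being "spontaneously breathing with face mask, nasal prong oxygen including high flow, or room air". Section 10.8 repeats the list. Periods must last at least 48 h.

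Apart from line 4, ECMO appears only in Section 1.4, as "ECMO: Extracorporeal membrane oxygenation".

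The SAP compares VFDs with a two-sided permutation test of means at alpha 0.05. It names no analysis population and has no rule for withdrawal, missing data or ECMO.

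**The concern.** There are two separate problems.

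First, going on ECMO or having an SAE is something that happens to a patient during follow-up. It is not a decision to leave the trial. Both are related to outcome, and provider choice is exercised in a trial that Section 1.1 says cannot be blinded. If patients can be taken out for these reasons and nothing keeps them in the analysis, any loss would not be random and could differ by arm.

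Second, the VFD rule asks only how the patient is breathing. A patient whose gas exchange is supported by ECMO can breathe spontaneously on nasal oxygen and meet the definition. The score then treats a day on extracorporeal support as a good day.

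At stake is the efficacy signal. Section 1.1 lists VFDs as secondary, but Aim 2 in Section 1.2 labels them primary within that aim, and theirs is the only test in the SAP with a stated alpha. With 20 patients, one or two scores carry weight. The temperature outcomes are not affected.

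**Working it through.** **Step 1. Does line 4 mean leaving the trial or stopping treatment?**
- Line 7 of the same form separately asks whether cooling was completed, why it ended early and how many hours were given.
- The Adverse Event form separates stopping hypothermia or NMB (row 12) from discontinuing the study (row 13).
- The intervention period is about 54 h (Section 8), but line 4 runs to day 28. A patient going on ECMO on day 10 has no study treatment left to stop.

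So line 4 means trial exit. Sections 8 and 11 give criteria for ending hypothermia early. No section gives criteria for withdrawal from the trial.

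**Step 2. What VFD does a withdrawn patient get?** The score depends on vital status at day 28. If that status is known, the rule works whether or not line 4 is ticked. If it is unknown, Section 10.10 read literally gives 0, and the Day 28 form gives no score because only death forces 0. No text says that data collection ends at withdrawal, and none says that it continues.

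**Step 3. Trace an ECMO patient through the VFD rule.**
- Still receiving assisted breathing: no VFDs. The score is right.
- Dead before day 28: 0. The score is right.
- On ECMO, off assisted breathing for at least 48 h and for whole 0800-to-0800 days, alive at day 28: each such day counts. Nothing in Section 10.8, Section 10.10 or the forms prevents it.

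**Step 4. Size.** The plan states no VFD mean, SD or effect size, so there is no figure to reproduce. Inputs: 20 patients (Section 1.1 and SAP) at 1:1 (Section 3.3), so n is about 10 per arm. Days credited, arm means and numbers of patients affected are assumptions.

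*Crediting ECMO days.* If a patient would otherwise score 0 and is credited d days, the arm mean rises by d/n:

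| d | rise in arm mean (days) |
|---|---|
| 5 | 5/10 = 0.5 |
| 10 | 10/10 = 1.0 |
| 20 | 20/10 = 2.0 |

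The arithmetic ceiling is 28/10 = 2.8.

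*Loss of zero scores, only if withdrawal did end data collection.* Dropping k true zeros changes an arm mean m to m × n/(n − k):

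| m | k = 1 | k = 2 |
|---|---|---|
| 4 | 4.44 | 5.0 |
| 8 | 8.89 | 10.0 |
| 12 | 13.33 | 15.0 |

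*Effect on the SAP's test.* Assumed data: hypothermia 0, 0, 0, 8, 12, 15, 17, 19, 20, 22 (mean 11.3); control 0, 0, 0, 0, 0, 0, 4, 10, 14, 18 (mean 4.6). Exact two-sided permutation p-values:
- all 20 patients as scored: 0.079
- two hypothermia zeros each credited 10 days (mean 13.3): 0.014
- one hypothermia zero missing: 0.039
- two hypothermia zeros missing: 0.015

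This example starts close to 0.05. It shows that the test is sensitive to one or two patients, not that a shift of this kind is likely.

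**The case against.** The strongest reply is that line 4 only records a fact. After it, the form goes straight on to day-28 and day-90 items (survival, unassisted breathing, extubation, discharge) with no instruction to stop, although other forms here say STOP or skip when they mean it. Section 3.5 follows patients through the medical record after day 7. Death is also a listed withdrawal reason, yet it has a defined VFD of 0, so a tick on line 4 does not in itself mean a missing score. All of this stands. A reader might infer that a patient withdrawn at ECMO has no VFD; the documents do not say so.

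A reader might also infer that withdrawal removes SAEs from the worse arm. That is not supported. The event that triggers withdrawal is already logged, because study discontinuation is a box in that event's own column. Section 2.2.1.1.1 also confines its SAE definition to the first three study days. The definition in Section 12 has no such limit, but later events would be missed only if collection stopped.

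The ECMO case is narrow, since it needs a patient on ECMO, off assisted breathing and alive at day 28. It is nevertheless what the written rule produces, and the form shows that ECMO was foreseen.

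Finally, one can produce an average bias by assumption. With 45% zeros and otherwise 1 to 24 days, deleting up to two zeros from an arm of 10 moves the mean from 6.86 to 8.53. That figure depends on an assumed distribution and an assumed deletion, and is not an expected bias.

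**Conclusion.** The concern holds in two limited parts.

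- **Withdrawal.** Outcome-dependent events and unblinded provider choice are listed reasons for trial exit, and no text keeps those patients in follow-up and analysis. Loss of their VFDs is possible, not established.
- **ECMO scoring.** The stated rule gives a wrong score for a defined, uncommon kind of patient. Each one credited 5 to 20 days instead of 0 adds 0.5 to 2.0 days to an arm mean, assuming 10 per arm and that all the credited days were spent on ECMO. The direction of any bias depends on which arm has such patients.

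The documents give no ECMO frequency and no VFD values, so the expected bias cannot be estimated. The point should be fixed before the data are analysed. It bears on the VFD comparison and not on the temperature outcomes.

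**What to change.** 1. In Section 10.8, the Unassisted Breathing Checklist and the SAP, state that any day with ECMO is not ventilator-free. No form has a field for ECMO start and stop dates, so add one.
2. On line 4, limit withdrawal from the trial to refusal of further participation or data use by the patient or LAR. Record ECMO, SAEs and provider decisions as dated events. Do not simply relabel line 4 as early stopping of the intervention: line 7 already records that, and the label could not describe ECMO or an SAE after the roughly 54 h treatment period.
3. In the SAP, state that all randomised patients are followed through the planned day-28, 60 and 90 contacts and analysed as assigned. Say how an unknown day-28 status is scored, and make Section 10.10 and the Day 28 form agree.

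The cost is CRF and SAP wording plus one added field; the contacts are already scheduled in Section 6. The downside is slightly lower VFDs for any ECMO patients.

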Pilot Randomized Clinical Trial of Therapeutic Hypothermia Plus Neuromuscular Blockade vs. Standard of Care in Patients With Moderate to Severe ARDS - the Cooling to Help Injured Lungs (CHILL) Pilot Study

NCT03376854

Statistical Analysis Plan

Date: May 19, 2020

Statistical Analysis Plan: This is a pilot study of feasibility to demonstrate feasibility and safety to treat patients with COVID-19 and ARDS with our CHILL treatment protocol (hypothermia to core temperature 34-35°C + NMB for 48h) and to determine whether there are any trends toward benefit in the treated group. The primary outcome will be analyzed using descriptive statistics, the mean \pm SD and the median \pm IQR of time to reach the target temperature and the percent of total treatment time within the targeted temperature range. Differences in SAEs will be analyzed by Chi square. The group difference on 28-day VFDs will be tested with a permutation test for the difference in group means with alpha = .05 (two-tailed). This test was chosen due to the large number of zero values expected (based on our open-label pilot and retrospective studies). If the difference on a baseline prognostic variable is statistically significant, we will perform a secondary analysis to adjust for this variable using a regression approach. For secondary clinical outcomes t-tests, Wilcoxon, or chi-square tests will be used as appropriate. Mixed model repeated measures ANOVA will be used to test for group differences for physiological and biomarker secondary outcomes over days 0, 1, 2, 3, 4, and 7. We will not include an interim analysis in this small RCT with only 20 subjects.

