
We have been approved for funding by Department of Defense (DoD) to support for a 4-year multicenter RCT of TH+NMB for 48h vs. standard of care with contract to be completed June 1, 2020 and with enrollment to begin in Fall of 2020. This study was designed prior to the onset of COVID-19, which is now the most common cause of ARDS and will likely continue to be in the Fall, 2020 and perhaps beyond. Therefore, it is important to decide whether patients with COVID-19 ARDS should be enrolled in our CHILL trial. Therefore, we will conduct a 20-patient pilot safety and feasibility trial of our CHILL TH+NMB treatment vs. control in COVID-19 patients with ARDS who meet the inclusion/exclusion criteria of our DoD-funded trial. The major objective of the proposed pilot trial is to determine whether it is safe and feasible to include patients with COVID-19 ARDS in our Phase IIb CHILL RCT of TH+NMB vs. control in patients with moderate to severe ARDS.

The pilot will be conducted at the University of Maryland Medical Center. To facilitate randomization within the inclusion window, we will consent and enroll based on partial fulfillment of randomization criteria and randomize once all criteria are met. Patients will be

eligible for enrollment when they have been diagnosed with COVID-19 by PCR, and have met all Berlin criteria for moderate to severe ARDS within the 48h inclusion window except the P/F ratio  $\leq 200$  but will not be randomized until P/F ratio (measured or imputed based on SpO2) is  $\leq 200$  (while on  $\geq 8$  cm H2O PEEP and  $\geq 0.6$  FiO2). We plan to randomize a total 20 patients over 4 months to hypothermia (core temperature 34°-35°C for 48h) plus NMB or usual temperature management. The primary outcome measures will be effectiveness of cooling in achieving and maintaining the target temperature and safety measures. Secondary outcomes will include 28-day ventilator-free days (VFDs), 28-day ICU-free days, oxygen saturation index (OSI), driving pressure, Sequential Organ Failure Assessment (SOFA) score, 60-day and 90-day survival, 90-day functional assessment, cognitive assessment at ICU and hospital discharge, and biomarkers of inflammation and lung injury. Since the nature of the intervention precludes blinding, all treatment and clinical decision making related to study outcomes will be protocolized and compliance with study protocols will be monitored.

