### 1.2/ Study Aims and Objectives

We will conduct the CHILL-pilot single-center RCT of TH in patients with COVID-19 and ARDS with P/F < 250 to address the following specific aims:

1. **Aim 1: Analyze the safety and feasibility and the potential lung protective effect of treating patients with COVID-19 infection and ARDS with P/F < 200 with mild TH (core temperature 34°-35°C) + NMB for 48h compared with controls receiving standard temperature management.** We expect the TH-treated group to achieve targeted temperature within 4h of randomization and to maintain TH for 48h without significant increase in serious adverse effects compared with the control arm.
2. **Analyze the potential lung protective effect of mild TH (core temperature 34°-35°C for 48h) and NMB in patients with ARDS and P/F < 200 compared with controls receiving standard temperature management.** We expect the TH-treated group to trend toward having more 28-day VFDs (primary) and 28-day ICU-FDs, and improved day-3 driving pressure and OSI than the controls.
3. **Evaluate the effects of TH on systemic inflammation and extrapulmonary organ dysfunction.** We expect the treated group to have reduced levels of proinflammatory mediators and lower Sequential Organ Failure (SOFA) scores than controls.

The proposed pilot study will determine whether we can safely include patients with COVID-19 and ARDS in our larger Phase IIb trial of TH and NMB in patients with ARDS. It will help us determine whether the 48h duration of cooling is sufficient.

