#### 10.5/ Day 2 and 3 Data CRFs

- Record site ID code, 3-digit study ID, and the unique 3 letter identifier in the indicated fields at the top of the worksheet.
- Record your name and the date and time CRF was completed in the indicated fields on line 1.
- Indicate vital status by checking appropriate Alive/Dead box on line 2 and, if “Dead,” record date and time of death in the indicated fields on line 3 and check the box next to the most appropriate cause of death (based on information from the discharge summary and discussion with the ICU provider team) on line 4.
- Indicate whether patient is still receiving NMB by checking appropriate “Yes/No” box on line 5 and, if “No,” record date and time it was discontinued on line 6, check the appropriate box for the major reason it was discontinued on line 7 (only check one box), and record the time neuromuscular function return (based on return of 4 twitches on train of 4 testing) in the indicated fields on line 8 or check the “no” box if neuromuscular function had not yet returned.
- Indicate whether the patient is in the hypothermia by checking the appropriate “Yes/No” box on line 9. If “No” skip to question 13. If “yes” indicate whether the patient is still being cooled as of 0800 of study day 2 (or 3) by checking the appropriate “Yes/No” box on line 10. If “Yes” skip to question 14. If “No,” record date and time cooling was stopped on line 11 and indicate the most closely applicable reason for discontinuing cooling by checking the appropriate box (check only one box) on line 12 and skip to line 14..
- For patients in the Control arm, indicate whether they received therapeutic hypothermia (intentional cooling to core temperature <36°C) since randomization by checking the appropriate Yes/No box on line 13. If in the hypothermia arm, check the “N/A” box.

- Indicate whether patient is still intubated (or if the patient has a tracheostomy, whether they are still receiving continuous mechanical ventilation (with <24h interruption) by checking appropriate yes/no box on line 14 and if “No” record date and time patient was extubated or was UAB for  $\geq 48$ h in the indicated fields.
- Indicate whether patient was started on renal replacement therapy (RRT) in the past 24 hours by checking appropriate “Yes/No” box on line 15. If the patient was already receiving RRT, check the N/A box.

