**Patient:**

Home Phone: -- Cell: --

Email: \_\_\_\_\_

**Legally Authorized Representative (Name):** \_\_\_\_\_

Home Phone: -- Cell: --

Email: \_\_\_\_\_

**Additional Contact 1:** Name: \_\_\_\_\_ Relationship to patient: \_\_\_\_\_

Home Phone: -- Cell: --

Email: \_\_\_\_\_

**Additional Contact 2:** Name: \_\_\_\_\_ Relationship to patient: \_\_\_\_\_

Home Phone: -- Cell: --

Email: \_\_\_\_\_

**Additional Contact 3:** Name: \_\_\_\_\_ Relationship to patient: \_\_\_\_\_

Home Phone: -- Cell: --

Email: \_\_\_\_\_

**Additional Contact 4:** Name: \_\_\_\_\_ Relationship to patient: \_\_\_\_\_

Home Phone: -- Cell: --

Email: \_\_\_\_\_

**Additional Contact 5:** Name: \_\_\_\_\_ Relationship to patient: \_\_\_\_\_

Home Phone: -- Cell: --

Email: \_\_\_\_\_

**Additional Contact 6:** Name: \_\_\_\_\_ Relationship to patient: \_\_\_\_\_

Home Phone: -- Cell: --

Email: \_\_\_\_\_

SITE ID		PATIENT ID				LETTER CODE			

## DAILY DATA – Day 01

(To be completed as close to 0800 as possible on the day after randomization)

Form Completed by \_\_\_\_\_            
MONTH D D Y Y Y Y TIME (0-

Vital status  Alive  Dead (If alive, skip to line 5)

Time of death:            
MONTH D D Y Y Y Y TIME (0-2400)

Cause of death (from discharge summary/discussion with ICU team), then skip to question 11.

- Respiratory failure  Cardiac (arrhythmia, ACS, cardiogenic shock)  Multi-organ failure  
 Refractory shock  Intraabdominal (perforation, compartment)  Withdrawal of care  
 Neurological devastation  Severe sepsis  Refractory acidosis  Hemorrhage

Is patient still receiving NMB?  Yes  No If "Yes" skip to question 9

Date/Time NMB discontinued:            
MONTH D D Y Y Y Y TIME (0-2400)

Reason for discontinuation:  Refractory bradycardia  Possible drug reaction  
 Decision of ICU provider  Decision of family

Date/Time: neuromuscular function (4 twitches/TOF) returned:            
or  Did not return MONTH D D Y Y Y Y TIME (0-2400)

Is patient in hypothermia group?  Yes  No If "No" skip to question 14

Minutes to reach 35°C from randomization:    from initiation of cooling:

Still being cooled?  Yes  No If "Yes" skip to question 15

If No, when was cooling stopped?            
MONTH D D Y Y Y Y TIME (0-2400)

Reason for discontinuation:  Refractory bradycardia with hypotension  Hemorrhage  

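### The primary cooling summaries have no rule for patients who never reach target or stop early, and none measures Aim 1's 4 h and 48 h expectation, so feasibility could be overstated

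*SAP*

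**What the plan says.** Protocol Section 1.1 makes cooling a primary outcome: "The primary outcome measures will be effectiveness of cooling in achieving and maintaining the target temperature and safety measures". On size it states "We plan to randomize a total 20 patients over 4 months"; with the 1:1 allocation in Section 3.3, that is about 10 patients in the TH arm. Section 1.2, Aim 1, sets the expectation: "We expect the TH-treated group to achieve targeted temperature within 4h of randomization and to maintain TH for 48h".

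The SAP states "The primary outcome will be analyzed using descriptive statistics", namely the mean with SD and the median with IQR "of time to reach the target temperature and the percent of total treatment time within the targeted temperature range". It attaches no confidence interval, proportion or threshold to the cooling outcome; its alpha is given for 28-day ventilator-free days only. It is silent on three things:

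- what value a patient who never reaches target receives;
- whether time to target runs from randomisation or from the start of cooling (Protocol Section 10.4 records both);
- what total treatment time means.

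Early stopping is foreseen. Section 8 lists criteria for ending hypothermia early, and the daily forms also offer provider and family decisions as reasons.

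The case report forms collect a good deal. Line 10 of the Day 01 form asks for "Minutes to reach 35°C from randomization" and the same interval from the start of cooling, with no option for target not reached. Sections 10.4 to 10.6 record the highest and lowest core temperature in each 2 h block. Line 10 of the Day 04 form records completion of 48 h. Line 7 of the Summary of Patient Outcomes records protocol completion, the reason for early termination and total hours cooled.

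**The concern.** The pilot is meant to inform whether COVID-19 patients can be included in the larger Phase IIb trial, so the cooling summary has to show failures as clearly as successes. A mean and SD of time to target cannot be computed with an undefined value, and the easiest course for an analyst is to leave the non-reacher out. The percentage in range depends on its denominator: over hours actually cooled, the hours lost after an early stop disappear from the calculation. The summary a reader would look for first, how many patients did what Aim 1 expected, is not planned. With so few patients in an unblinded trial, these choices should not be left until the data are visible.

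**Working it through.** The plan gives no derived figure to reproduce: N = 20 comes without a power or precision basis. The calculations below show the consequence of the missing rules. The arm size follows from the documents (20/2 = 10). Reach times, stopping times and reach rates are assumptions.

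**Non-reachers.** Suppose eight patients reach target at 2, 2.5, 2.5, 3, 3, 3.5, 3.5 and 3.5 h, and two never do.

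- Reachers only: mean = 23.5/8 = 2.9 h, median 3.0 h, 8/8 within 4 h.
- All ten: no mean exists. With non-reachers ranked last, the median is (3 + 3.5)/2 = 3.25 h, and 8/10 are within 4 h.

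The ranked median moves only from 3.0 to 3.25 h, so it does not reveal the failures by itself; the proportion does. If every reacher reaches within 4 h:

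| Never reach, of 10 | Reachers only within 4 h | All randomised to TH | Exact (Clopper-Pearson) 95% CI |
|---|---|---|---|
| 0 | 100% | 100% | 69.2–100% |
| 1 | 100% | 90% | 55.5–99.7% |
| 2 | 100% | 80% | 44.4–97.5% |
| 3 | 100% | 70% | 34.8–93.3% |
| 4 | 100% | 60% | 26.2–87.8% |

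The chance of at least one non-reacher among 10 is 1 − p^10, where p is the true reach rate: 40% at p = 0.95, 65% at 0.90 and 89% at 0.80.

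**Early stopping.** Assume a 3 h lead-in to target and perfect maintenance afterwards. The score over hours cooled is (stop − 3)/stop; over the planned period it is (stop − 3)/48.

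| Cooling stopped at | Over hours cooled | Over 48 h |
|---|---|---|
| 6 h | 50% | 6.2% |
| 12 h | 75% | 18.8% |
| 24 h | 87.5% | 43.8% |
| 48 h (completer) | 93.8% | 93.8% |

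With eight completers and two patients stopped at 12 h:

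- hours cooled: (8 × 93.75 + 2 × 75)/10 = 90.0%;
- planned 48 h: (8 × 93.75 + 2 × 18.75)/10 = 78.75%.

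The gap is 11.25 points. The arm median is 93.75% either way, so the median hides the two stoppers under both denominators.

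If the lead-in is excluded, a stopper who stays in range scores 100% over hours cooled. With eight completers at an assumed 85% and two patients stopped after 6 in-range hours, the means are (8 × 85 + 2 × 100)/10 = 88.0% over hours cooled and (8 × 85 + 2 × 12.5)/10 = 70.5% over 48 h, a gap of 17.5 points.

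**Start of the 48 h.** In Protocol Section 8, the description of the TH arm can be read as 48 h of maintenance after target is reached, while the order-entry text times rewarming from initial cooling. For a perfect completer with a 3 h lead-in, the first reading gives 48/48 = 100% and the second 45/48 = 93.75%. The two passages must be reconciled before any 48 h denominator can be applied.

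**The case against.** The strongest reply is that silence is not a defect of direction. A reader might infer four stronger things, and the documents do not support them.

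- *That the SAP excludes non-reachers.* It does not say so. Omission is only the likely default for a mean; the planned median could keep them, ranked last.
- *That both measures flatter failed cooling.* A patient who is cooled but never enters the range scores 0% in range, whether over hours cooled from the start of cooling or over 48 h. Eight patients at 85% and two at 0% average 68%, so the second measure does register that failure.
- *That early stopping is rewarded.* The SAP itself describes the treatment as lasting 48 h, so total treatment time may mean the planned period, which penalises stopping in full. Over hours cooled from the start of cooling, with the same lead-in and perfect maintenance, a stopper still scores below a completer (75% against 93.8%). Matching or beating a completer on those terms requires leaving the lead-in out.
- *That slow coolers are lost.* The Day 1 window lasts at least 8 h 1 min (schedule notes on the randomisation form), so it always covers the 4 h point. First entry into range after Day 1 can be derived, to about 2 h, from the block temperatures.

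Two further replies also stand. Aim 1 states an expectation, with no go/no-go rule, so the right criticism is that it is not assessed, rather than not tested. And counting hours after stopping as out of range mixes temperature control with tolerability, so that figure should not stand alone.

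None of this supplies the missing rules. The SAP does not choose a denominator or a clock, does not name the completion fields, and plans no proportion.

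**Conclusion.** The concern holds as a gap in specification. The SAP does not say how cooling failures enter its primary summaries. Under the likely default (non-reachers omitted from the mean) and one possible reading (total treatment time as hours cooled), the results would look better than the cooling was. It also plans nothing against the 4 h and 48 h expectation.

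The size depends on assumed data. Two non-reachers of 10 turn 80% within 4 h (CI 44.4–97.5%) into an apparent 100%. Two patients stopped at 12 h raise the mean time in range by about 11 points. If the planned 48 h is what the SAP means, the second effect vanishes; if everyone reaches target and completes, neither arises. The documents support saying that feasibility could be overstated, not that it will be.

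**What to change.** First reconcile the two statements in Protocol Section 8 on when the 48 h begins. Then specify in the SAP, for all patients randomised to TH:

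1. the number and proportion reaching 34–35°C within 4 h of randomisation, non-reachers counted as failures, with an exact 95% CI;
2. time to target from randomisation as a median with non-reachers ranked last, or by Kaplan-Meier, in place of the mean and SD;
3. percent of time in range over the planned 48 h, reported beside the proportion completing 48 h and the hours cooled, so that temperature control and early stopping can be read separately.

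The data are already collected, so no new form field is essential; repeating the time-to-target field after Day 1 would only be a convenience. The cost is SAP wording and slightly more analysis, and the reported figures may be less favourable.
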